9.0 CRITERIA FOR EVALUATION AND ENDPOINT DEFINITIONS

Patients who complete radiation therapy and 1 cycle (12 weeks) of androgen deprivation treatment on protocol will be included in analysis of tumor response and time to PSA relapse

- 9.1 Disease Status
 - 9.1.1 Measurable disease: Lesions that can be accurately measured in at least one dimension by 1) medical photograph (skin or oral lesion), palpation, plain X-ray, CT, MRI, or other conventional technique with longest diameter 2 cm or greater in the axial plane (bone lesions not included), or 2) spiral CT with longest_diameter 1 cm or greater. Ultrasound is only suitable for superficial disease (superficial palpable nodules, subcutaneous lesions, thyroid lesions). Conventional CT and MRI should be performed with cuts of 10 mm or less in slice thickness contiguously. Spiral CT should be performed using a 5 mm contiguous reconstruction algorithm.
 - 9.1.2 Non-measurable disease: Lesions too small to be considered measurable, masses with margins not clearly defined, bone disease, pleural or pericardial disease, leptomeningeal disease, pneumonitis, lymphangitis.
- 9.2 Objective Status

(To be recorded at each evaluation.) All measurable lesions (patients eligible for this protocol will have no more than 5 metastases) should be identified at baseline. Measurements must be provided for all measurable lesions, while presence or absence must be noted for non-measurable disease. Unless progression is observed, objective status can only be determined when all measurable and non-measurable sites and lesions are assessed.

- 9.2.1 Partial response in non-measurable disease (PRNM). Decrease in PSA level of > 50% compared to baseline pre-treatment level. No progression of non-measurable disease. No new lesions.
- 9.2.2 Partial response (PR): Applies only to patients with at least one measurable lesion. Greater than or equal to 30% decrease under baseline in the sum of longest diameters of all target measurable lesions. No progression of non-measurable disease. No new lesions. All measurable and non-measurable lesions and sites must be assessed using the same techniques as baseline.
- 9.2.3 Complete response (CR): Complete disappearance of all measurable and non-measurable disease. No new lesions. No disease-related symptoms. For patients status post previous prostatectomy PSA level <0.2. For patients with remaining prostate declining or stable PSA level <1. All measurable, and non-measurable lesions and sites must be assessed using the same technique as baseline.

- 9.2.4 Stable/No response: Does not qualify for CR, PR, or progression. All measurable and non-measurable sites must be assessed using the same techniques as baseline.
- 9.2.5 Progression: One or more of the following must occur **at the time of androgen deprivation therapy:** Increase in PSA by 25% over baseline (to at least > 2 ng/ml), 20% increase in the sum of longest diameters of target measurable lesions over smallest sum observed (over baseline if no decrease during therapy) using the same techniques as baseline, clear worsening of any non-measurable disease, reappearance of any lesion that had disappeared, appearance of any new lesion/site, failure to return for evaluation due to death, deteriorating condition (unless clearly unrelated to this cancer).
- 9.2.6 a) Non-measurable disease does not affect objective status except in determination of CR (must be absent a patient who otherwise has CR, but who has non-measurable disease present or not assessed, will be classified as having a PR), and in determination of progression (if new sites of disease develop or if unequivocal progression occurs in the opinion of the treating physician).

b) Appearance or worsening of pleural effusions do not constitute unequivocal progression unless cytologically proven of neoplastic origin.

c) For "scan-only" bone disease, increased uptake in previously seen lesions does not constitute clear worsening.

d) In cases for which initial tumor flare reaction is possible (hypercalcemia, increased bone pain, erythema of skin lesions), either symptoms must persist beyond 4 weeks or there must be additional evidence of progression.

e) Lesions that appear to increase in size due to presence of necrotic tissue will not be considered to have progressed.

9.2.7 Unknown: Progression has not been documented and one or more measurable or non-measurable sites have not been assessed.

- 9.2.8 PSA relapse after completion of initial 36 weeks of androgen deprivation therapy is defined as an increase in PSA value to above pre-therapy level or > 10 (whichever is smaller). For example patient with pre-treatment PSA level of 40 will resume androgen deprivation therapy when PSA level is > 10, patient with pre-treatment PSA level of 3 will resume androgen deprivation therapy when PSA level is > 3.
- 9.3 Best Response: This is calculated from the sequence of objective statuses
 - a) CR: Two or more objective statuses of CR a minimum of four weeks apart documented before progression or symptomatic deterioration.
 - b) PR: Two or more objective statuses of PR or better a minimum of four weeks apart documented before progression or symptomatic deterioration, but not qualifying as CR.
 - c) Unconfirmed CR: One objective status of CR documented before progression or symptomatic deterioration but not qualifying as CR or PR.
 - d) Unconfirmed PR: One objective status of PR documented before progression or symptomatic deterioration but not qualifying as CR, PR or unconfirmed CR.
 - e) Stable/no response: At least one objective status of stable/no response documented at least six weeks after registration and before progression or symptomatic deterioration, but not qualifying as anything else above.
 - f) Increasing disease: Objective status of progression or symptomatic deterioration within twelve weeks of registration, not qualifying as anything else above.
 - g) Inadequate assessment, response unknown: Progression or symptomatic deterioration greater than twelve weeks after registration and no other response category applies.
- 9.4 Time-Related Endpoint Definitions
 - 9.4.1 Survival: Defined as the time from registration to time of death due to any cause. If a patient is not known to have died, survival time is censored at the time of last follow-up.
 - 9.4.2 Progression-free survival: Defined as the time from registration to the first observation of disease progression (as defined in 9.2.5) or death due to any cause. If a patient has not progressed or died, progression-free survival is censored at the time of last follow-up.
 - 9.4.3 Time to treatment failure: Defined as the time from registration to the first observation of disease progression, death due to any cause, or early discontinuation of treatment. If failure has not occurred, failure time is censored at the time of last follow-up.
 - 9.4.4 Time to PSA relapse: Time from the date of the last dose of bicalutamide or the last day of radiation therapy (whichever comes later) until the date the criteria are met for the PSA relapse (see 9.2.8)

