5.0 ELIGIBILITY CRITERIA

5.1 Inclusion Criteria

- 5.1.1 Patients with histologically proven diagnosis of adenocarcinoma of the prostate stage N1, N2, N3, M1a, M1b, M1c with \leq 5 metastatic lesions. If the diagnosis of metastasis in the lymph node is based solely on imaging CT scan or MRI, the longitudinal diameter of the lymph node has to be \geq 2.0 cm. If the lymph node is positive on PET or Prostascint scan, the longitudinal diameter of the lymph node on CT scan or MRI has to be \geq 1.5 cm.
- 5.1.2 Patients who have measurable disease must have had X-rays, scans or physical examination used for tumor measurement completed within 28 days prior to registration. Patients must have non-measurable disease assessed within 42 days prior to registration.
- 5.1.3 Patients must have had documented PSA level of > 2 prior to onset of androgen deprivation.
- 5.1.4 Patients might have received up to 36 weeks of adjuvant androgen deprivation therapy and up to 36 weeks of androgen deprivation therapy for metastatic disease prior to enrollment to this study. Patients may be on androgen deprivation for metastatic disease at the time of enrollment to the protocol. Adjuvant therapy must have been completed at least 2 years before

androgen deprivation for metastatic disease and patients must remain hormone sensitive.

- 5.1.5 Prior radiation therapy for metastatic disease is not allowed.
- 5.1.6 Prior chemotherapy for metastatic disease is not allowed. Prior neoadjuvant and adjuvant chemotherapy is allowed. Patients must have recovered from all acute side-effects related to previous systemic therapy.
- 5.1.7 Patients are allowed to receive one prior systemic non-chemotherapeutic treatment (i.e. immunotherapy, receptor tyrosine kinase inhibitor, antiangiogenic agent, differentiating agent) for recurrent or metastatic disease. Patients must have recovered from all acute side-effects related to previous systemic therapy.
- 5.1.8 Use of bisphosphonates is allowed at the discretion of treating physician
- 5.1.9 Patients must be at least 18 years of age.
- 5.1.10 Patient must be capable of understanding the nature of the trial and must give written informed consent.
- 5.1.11 Patients must have a WHO Performance status of 0, 1, or 2.
- 5.2 Exclusion Criteria
 - 5.2.1 Patients with unstable or severe intercurrent medical conditions or active, uncontrolled infection.
 - 5.2.2 Patients with history of orchiectomy.

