10.0 STATISTICAL CONSIDERATIONS

This is a phase II study to evaluate the efficacy and safety of radiation to metastatic sites plus 36 weeks months of androgen deprivation in patients with hormone-sensitive prostate cancer. The primary endpoint in this trial will be time to PSA relapse as defined in 9.2.8 and 9.4.4. Secondary endpoints include PSA response to treatment, safety, feasibility and tolerability.

Based on the prior data, the median time to PSA relapse (PSAR) following 36 weeks of androgen deprivation therapy, is approximately 40 weeks. This study would then look to detect an improvement beyond 40 weeks. For a one-sample, one-sided, 0.05-level test using the large-sample normal approximation for the distribution of the logarithm of the maximum likelihood estimator of the exponential parameter, with 28 patients and assuming accrual of 24 months and follow-up of 12 months, there will be 83% power for the test of the null hypothesis that the median PSAR is 9 months vs. the alternative that the median PSAR is 16 months as measured from the end of the twelve months of androgen deprivation therapy. If the parametric estimate of median PSAR is 13 months, this would suggest activity for the addition of radiation therapy. The initial analysis will include all patients, although analysis by strata will also be conducted in an exploratory fashion as will the role of previous adjuvant hormone treatment.

In addition to obtaining an early estimate of the effect of this therapy based on survival, feasibility and toxicity will also be carefully monitored in this novel approach.

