10.1 Interim analysis for toxicity

With 28 patients, we will be able to estimate the complication rate (any grade 3 or higher toxicity attributable to the radiation or combination of androgen deprivation/ radiation therapy) with a maximum standard error of 19%. If less than 2 cases have radiation induced complications, we can rule out a 17% complication rate or higher with 95% confidence. Since this therapy is not expected to cause severe toxicities, if at any time more than 25% of the patients experience a radiation induced complication, the study will be halted pending review.

The outcome status (in terms of toxicity, response, reason off study, progression, and survival) of all eligible patients who are registered will be reported. All patients who receive any treatment will be included in the summaries of toxicities. The CTCAE v. 3.0 toxicity criteria will be used. Toxicity information recorded will include the type, severity, time of onset, time of resolution, and the probable association with the study regimen. Time to progression and overall survival will be estimated using the product-limit method of Kaplan and Meier.

The sample-size, as justified above, is 28 patients. With an expected accrual of 14 patients per year, it will take approximately two years to complete the accrual.

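### Section 9.0's on-protocol completion rule, read literally, removes nearly all of Stratum 2 and does not fit Section 10.0's all-patients analysis and its power on all 28

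*Combined protocol and SAP*

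**What the plan says.** The opening of Section 9.0 (Criteria for Evaluation and Endpoint Definitions) requires completed radiotherapy (RT) and one 12-week cycle of ADT on protocol: "Patients who complete radiation therapy and 1 cycle (12 weeks) of androgen deprivation treatment on protocol will be included in analysis of tumor response". It applies that rule to both outcomes: "androgen deprivation treatment on protocol will be included in analysis of tumor response and time to PSA relapse". Section 10.0 names time to PSA relapse as the primary endpoint. The phrase *on protocol* is not defined.

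Entry is deliberately wide. Section 5.1.4 allows "up to 36 weeks of androgen deprivation therapy for metastatic disease prior to enrollment to this study". Section 6.1.2 counts those weeks toward one 36 (±2) week course, so a patient with 12 prior weeks receives 24 more. Stratum 2 holds patients who enrol near the end of the 36 weeks, or after it, when RT can no longer finish before ADT does. Their total ADT may not exceed 36 weeks.

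Section 10.0 describes the analysis differently: "The initial analysis will include all patients, although analysis by strata will also be conducted in an exploratory fashion". Its power statement reads "with 28 patients and assuming accrual of 24 months and follow-up of 12 months, there will be 83% power". Section 10.1 adds "The sample-size, as justified above, is 28 patients" and expects about two years of accrual at 14 per year, so 28 is the number enrolled. No allowance for unevaluable patients appears. Section 10.1 also promises that "The outcome status (in terms of toxicity, response, reason off study, progression, and survival) of all eligible patients who are registered will be reported".

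**The concern.** The protocol enrols a stratum by design and plans to analyse it, yet a literal reading of Section 9.0 removes almost all of it from the primary analysis. Two analysts could each follow the text and report the median time to PSA relapse on different patients, one with Stratum 2 and one nearly without it. In a single-arm trial of 28 judged against a historical 9-month median, that choice should not be open once results are visible. Under any reading that excludes patients, fewer than 28 contribute and the power is lower than stated.

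**Working it through.** **1. Who the literal rule excludes.** Inputs: total ADT of 36 (±2) weeks (6.1.2), and 12 weeks required on protocol (9.0).

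- Latest entry that still leaves 12 weeks: 36 − 12 = week 24. With the window, 34 − 12 = 22 to 38 − 12 = 26.
- A patient enrolling after completing ADT has 0 on-protocol weeks and is always excluded.
- A Stratum 2 patient enrolling with exactly 12 weeks left belongs to that stratum only if RT overruns the end of ADT. The Section 8.0 calendar gives RT of 2 to 7 weeks, so RT would have to start more than 12 − 7 = 5 weeks (7-week course) to 12 − 2 = 10 weeks (2-week course) after enrolment. Few patients would fit.
- A Stratum 1b patient with more than 24 prior weeks is also excluded, even if a short RT course finishes before week 36.

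The prostate figures in 6.2.5 (7500 to 7800 cGy at 180 to 200 cGy/day) imply 37.5 to 43.3 fractions, or 7.5 to 8.7 weeks at an assumed five per week. That is longer than the calendar's 7 weeks and would shorten the 5-week delay to about 3.3 to 4.5 weeks. The two sections need reconciling, but the conclusion here does not change.

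**2. The readings side by side.**

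| Reading of *on protocol* | Stratum 2 | RT non-completers | Fit with 10.0 and 10.1 |
|---|---|---|---|
| Weeks after enrolment (literal) | Nearly all excluded | Excluded | Conflicts with all patients, by-strata analysis and 28 |
| Protocol-type ADT, prior weeks credited | Kept | Excluded | Strata fit; 28 has no allowance for exclusions |

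If *all patients* in 10.0 means only that strata are pooled among evaluable patients, the literal rule still leaves almost nothing to analyse in Stratum 2.

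**3. The plan's power figure.** Inputs from 10.0: one-sample exponential test on the log of the maximum likelihood estimate, one-sided 0.05, medians 9 and 16 months, accrual a = 24, follow-up f = 12, n = 28.

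- P(event) = 1 − [exp(−λf) − exp(−λ(a+f))]/(λa), with λ = ln 2/median. This gives 0.819 at 9 months and 0.630 at 16 months.
- Expected events: d0 = 28 × 0.819 = 22.94 and d1 = 28 × 0.630 = 17.65 (unrounded probabilities used).
- Critical median = 9 × exp(1.645/√22.94) = 12.69 months.
- Power = Φ(ln(16/12.69) × √17.65) = 83.5%.

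This matches the stated 83%. Using the alternative's variance throughout gives 78.0%, and the null's throughout 86.7%; neither matches at 28.

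**4. The same calculation with fewer analysed.** The documents give no Stratum 2 share and no drop-out rate, so these counts are assumptions.

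| Analysed (excluded) | d0 | d1 | Power |
|---|---|---|---|
| 28 (0) | 22.94 | 17.65 | 83.5% |
| 25 (3) | 20.48 | 15.76 | 80.0% |
| 24 (4) | 19.66 | 15.13 | 78.7% |
| 21 (7) | 17.20 | 13.24 | 74.2% |

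**The case against.** The best defence is that *on protocol* simply means ADT of the type the protocol specifies. Section 6.1.2 counts prior weeks toward one course, the treatment schema and 6.1.2 admit late entrants on purpose, and 10.0 plans an analysis by strata. Crediting prior ADT fits all three and keeps Stratum 2. This is plausible, and it means the loss of Stratum 2 is a consequence of the literal wording rather than a demonstrated intention. It does not close the point: the phrase is undefined, the RT-completion exclusion remains, and 28 is still the full accrual.

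It can also be said that early failures are not lost. Section 10.1 reports the outcome status of all eligible registered patients, and progression-free survival and time to treatment failure (9.4.2, 9.4.3) run from registration. That is true, but those are other endpoints or descriptive reporting, and they do not settle the primary set.

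A reader might infer that with 24 or fewer analysed, an estimate at the activity bar would no longer be significant, since Section 10.0 says "If the parametric estimate of median PSAR is 13 months, this would suggest activity for the addition of radiation therapy" and the critical median at 24 is 13.04 months. The documents do not support attributing this to Section 9.0. That figure uses the events expected under a 9-month median. With the events expected at a 13-month median (0.7025 per patient, 19.7 events from 28), z = ln(13/9) × √19.7 = 1.63 and one-sided p = 0.051 with nobody excluded. If the 12 months ran from registration with an assumed 36-week lag to time zero, minimum follow-up would be about 3.7 months and the critical median with all 28 would be 13.2 months. The threshold depends on the variance and follow-up convention.

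**Conclusion.** The concern holds as an inconsistency in the primary analysis set and should be fixed. Sections 9.0 and 10.0 cannot both be followed if 9.0 is read literally. If prior ADT is credited, the conflict shrinks to an unallowed exclusion of patients who do not complete RT. The text does not choose between the two.

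The size is uncertain. Against 83.5% with all 28, losing three to seven patients brings power to between 80.0% and 74.2%, on the protocol's own medians, accrual and follow-up, with the number lost assumed.

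Two stronger inferences are not supported. The 83% is not a miscalculation; it is correct for 28 analysed. Nor is the response rate shown to be inflated. Requiring completed RT drops non-normalizers, progressors and toxicity drop-outs, which favours a higher rate. The 12-week rule drops late entrants, and those who reach RT have already normalized their PSA, so it may act the other way. The net direction is not established.

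**What to change.** Replace the opening sentence of 9.0 and cite the new definition in 10.0.

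- **Primary endpoint:** all eligible patients in both strata who start protocol RT and reach the time zero in 9.4.4, with no minimum number of ADT weeks after enrolment. Report how many registered patients never reach time zero, and why. Keep the present 9.0 set as a sensitivity analysis, stating whether pre-enrolment ADT counts.
- **Response:** all eligible registered patients as the denominator, consistent with 10.1, counting undocumented response as non-response. Show results by stratum, because late entrants may have had their PSA response before enrolment.
- **Power:** state in 10.0 whether 28 means enrolled or evaluable, and restate the power for the number expected to be evaluable. The proposed primary set still omits patients who never start RT, so this is needed in any case.

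The cost is mainly wording and one recalculated figure. A censoring rule is also needed for patients who stop early, since 9.2.8 defines relapse only after 36 weeks of ADT are complete and only chart review is planned once patients are off protocol. Power and response figures may look slightly less favourable. If the sponsor prefers to keep 28 evaluable, enrolment becomes 28/0.90, rounded up to 32, or 28/0.75, rounded up to 38, for an assumed 10% or 25% excluded. At 14 per year that is about 2.3 or 2.7 years instead of 2.

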6.0 TREATMENT PLAN

Treatment will be given according to the Schema described in section 6.1. A treatment may be stopped for up to 4 weeks to allow for recovery from toxicities. Patients unable to safely resume treatment at that point will be taken off study. 12 weeks constitutes one cycle of hormone therapy.

6.1 Treatment schedule:

- 6.1.1 Patients will begin radiation therapy only after they have demonstrated evidence of PSA normalization after initiation of androgen deprivation therapy (stable or declining PSA level of \leq 4 (or stable or declining PSA \leq pre-treatment level whichever is smaller) on two consecutive measurements. Patients who do not meet these criteria will be taken off protocol.
- 6.1.2 Patients will be divided into two strata:

Stratum 1:

a) Patients who are not on androgen deprivation therapy at the time of enrollment to the protocol will begin androgen deprivation and start radiation therapy after PSA normalization (see section 6.1.1)

b) Patients who are already treated with androgen deprivation therapy at the time of enrollment to the protocol (see 5.1.4) will continue androgen deprivation therapy and begin radiation after meeting criteria for PSA normalization (see section 6.1.1). Radiation therapy will be finished before 36 weeks (± 2 weeks) of hormone therapy is completed.

Stratum 2:

Patients who are enrolled on the protocol towards the end (or after completion) of 36 weeks (\pm 2 weeks) of androgen deprivation so radiation treatment cannot be finished before the completion of 36 weeks of androgen deprivation therapy can still initiate and/or complete radiation therapy as long as their serum testosterone level remains at the castrated levels (<50 ng/dL) and they meet the criteria for PSA normalization (section 6.1.1). Patients will not receive more than 36 weeks of androgen deprivation therapy.

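### Among irradiated patients, the PSA rule for starting radiation sets a floor under the PSA response rate, and that rate cannot inform on radiation

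*Combined protocol and SAP*

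**What the plan says.** Objective 2 in section 1.0 is to assess PSA and objective response to 36 weeks of androgen deprivation therapy (ADT) plus radiotherapy. Section 10.0 carries this forward: "Secondary endpoints include PSA response to treatment, safety, feasibility and tolerability". It gives PSA response no definition, null rate or target. The plan has only one criterion based on a percentage fall in PSA: "Decrease in PSA level of > 50% compared to baseline pre-treatment level". It sits in section 9.2.1, under partial response in non-measurable disease (PRNM), which also requires that such disease has not progressed and that no lesion has newly appeared.

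Section 6.1.1 decides who is irradiated: "Patients will begin radiation therapy only after they have demonstrated evidence of PSA normalization after initiation of androgen deprivation therapy". Normalization means a stable or falling PSA no higher than 4, or no higher than the pre-treatment level, "whichever is smaller) on two consecutive measurements. Patients who do not meet these criteria will be taken off protocol".

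Section 9.0 then sets the analysis population for tumor response and time to PSA relapse: "Patients who complete radiation therapy and 1 cycle (12 weeks) of androgen deprivation treatment on protocol will be included in analysis". Section 10.1 says something different: outcome status, including response and reason off study, is to be reported for every eligible registered patient.

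On entry PSA, section 5.1.3 requires only this: "Patients must have had documented PSA level of > 2 prior to onset of androgen deprivation". Sections 5.1.4 and 6.1.2 allow enrollment during ADT for metastatic disease, or after it has been completed.

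**The concern.** The rule for starting radiation and the response criterion use the same marker, and the rule is applied first. A patient whose PSA began well above 4 and has come down to 4 or less has already had a large fall. A patient who has not come down is removed, and under section 9.0 also leaves the response analysis. The response rate in the remaining patients is then partly fixed by who was allowed to stay.

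This is a single-arm trial, and section 10.0 asks whether adding radiation shows activity. A high PSA response rate in irradiated patients could be read as support for radiation, although the fall came before any radiation was given. In patients enrolled during or after ADT, some or all of the fall may also predate registration.

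**Working it through.** **The plan's own figures.** The plan states no PSA response rate, so there is none to reproduce. Its one power figure, 83% for time to PSA relapse with 28 patients, does reproduce. With 22.9 expected events under a 9-month median and 17.6 under 16 months, power = Φ((ln(16/9) − 1.645/√22.9) × √17.6) = 83.5%. PSA response does not enter that calculation.

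**Inputs.**
- Ceiling for starting radiation: the smaller of 4 and the pre-treatment PSA (6.1.1).
- PSA part of PRNM: a fall of more than 50% from the pre-treatment level (9.2.1).
- Entry: pre-ADT PSA above 2 (5.1.3).
- Analysis set: patients who complete radiation and 12 weeks of on-protocol ADT (9.0), all of whom have met the ceiling.
- Pre-treatment level is read as pre-ADT level, as section 6.1.3 uses it.

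**Step 1: the fall that the ceiling forces.** For pre-ADT PSA P, the smallest possible fall in an irradiated patient is 1 − min(4, P)/P.

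| P | Forced fall | More than 50%? |
|---|---|---|
| 2.1 to 4 | 0% | no |
| 5 | 20% | no |
| 6 | 33.3% | no |
| 8 | 50.0% | no |
| 8.1 | 50.6% | yes |
| 10 | 60% | yes |
| 20 | 80% | yes |
| 40 | 90% | yes |

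For P above 4, 1 − 4/P > 0.5 holds exactly when P > 8. Above 8, a patient without a fall of more than 50% cannot be in the section 9.0 set.

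**Step 2: the rate in the section 9.0 set.** Let f be the share of that set with P > 8, and r the response rate in the others. The rate on the PSA part is S = f + (1 − f) × r, so its floor (r = 0) is f. The documents give neither f nor r. Assumed values:

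| f | Floor (r = 0) | r = 50% | r = 80% |
|---|---|---|---|
| 30% | 30% | 65% | 86% |
| 50% | 50% | 75% | 90% |
| 70% | 70% | 85% | 94% |
| 90% | 90% | 95% | 98% |

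**Step 3: all registered patients.** Let g be the share who fail the PSA rule, and q the proportion of those who nevertheless had a fall of more than 50%. Ignoring other exclusions, the rate is (1 − g) × S + g × q, so restricting to the section 9.0 set raises the rate by g × (S − q). With assumed g = 20% and S = 94% (f = 70%, r = 80%), that is 18.8 points if q = 0, and 0.20 × (0.94 − 0.50) = 8.8 points if q = 50%.

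The forced floor among registered patients is (1 − g) × f. At f = 70% it is 66.5%, 63%, 56% and 49% for g = 5%, 10%, 20% and 30%. Even at f = 100% it is 80% when g = 20%.

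**Step 4: late joiners.** Section 6.1.2 caps total ADT at 36 weeks. Read literally, a patient enrolling after more than 36 − 12 = 24 weeks of ADT (26 with the two-week tolerance) cannot complete 12 weeks on protocol and falls outside the section 9.0 set.

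**The case against.** A reader might infer that the PSA response rate is close to 100% by construction. The documents do not support that. Entry needs a PSA above 2, sections 6.1.3 and 9.2.8 both use a patient with PSA 3 as an example, and the ceiling forces no qualifying fall from above 2 up to 8. A forced rate of 95% would need 95% of analysed patients to have begun above 8, and no PSA distribution is given.

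A reader might also infer that the rate says nothing about the regimen. ADT is part of the regimen in Objective 2, so a fall on ADT is a response to it. What the rate cannot do is isolate radiation.

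Nor does the plan conceal patients who never normalize, since section 10.1 reports response and reason off study for all eligible registered patients. But it does not say whether the rate comes from 9.0 or 10.1, or how those patients are classified.

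Three further limits stand:
- PRNM also requires no progression of non-measurable disease and no new lesions, and the study calendar puts tumor evaluation at the end of ADT or radiation. Only the PSA part is met in advance.
- Section 9.0 names tumor response and time to PSA relapse. It reaches PSA response because the PSA criterion sits inside an objective-status category.
- The study calendar takes a PSA within 14 days of cycle 1 day 1. If that were the baseline for patients already on ADT, the forced fall would exceed 50% only where that value was above 8 (0% at 3, 33.3% at 6, 66.7% at 12).

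Late Stratum 2 joiners cannot be called responders at registration as a group: they too need a pre-ADT PSA above 8, and step 4 suggests many are outside the section 9.0 set.

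**Conclusion.** The point holds for the section 9.0 set and for the PSA part of PRNM. Every patient in that set with a pre-ADT PSA above 8 has met the PSA part before the first radiation fraction. The rate has a floor equal to the share of such patients and cannot inform on the radiation component. Sections 9.0 and 10.1 give two different denominators.

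This rests on three assumptions. Pre-treatment is taken to mean pre-ADT. A qualifying fall seen when radiation is cleared to start counts as response even if PSA later rises. The upward bias requires q < S, meaning that patients lost to the rule have a qualifying fall less often than those kept. The rule selects in that direction, but not perfectly: a fall from 100 to 6 is 94% and still fails the rule. The size cannot be fixed from the documents because f, r, g and q are all unstated.

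The endpoint is secondary and has no test attached. The primary endpoint and its power are unaffected.

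**What to change.** Amend sections 9.0, 9.2.1 and 10.0; section 6.1.1 need not change.

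1. Make all eligible registered patients the denominator for the PSA response rate, so that 9.0 agrees with 10.1. Classify each patient by observed PSA against the pre-ADT level. Patients taken off protocol for non-normalization without a fall of more than 50% count as non-responders. Show separately the patients already normalized on ADT at registration, whose fall predates the study.
2. In irradiated patients, report PSA change after radiation against the last pre-radiation value, as description only. ADT is still acting in most of these patients, so even this change is not attributable to radiation. Do not present the rate of falls greater than 50% from pre-treatment in this set as evidence for radiation. The PSA levels in the complete-response definition (9.2.3) would not serve instead, because they can be reached on ADT alone.

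The cost is wording: the study calendar already schedules PSA every 4 weeks for the first two years. The downside is a less favourable reported response rate.
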